8.2 TREATMENT COMPLIANCE

Study medication compliance for a specified period is defined as the total dose (mg) actually taken by a patient during that period divided by the prescribed dose expected to be taken during the same period multiplied by 100. Descriptive statistics for study medication compliance is presented.

9 CONCOMITANT MEDICATIONS

The World Health Organization Drug Dictionary (WHODD) Version 15 is used to classify concomitant medications by therapeutic class and preferred term based on ATC code level 3. Concomitant medication is defined as any medication taken between the day of first dose of the study medication and the day of last study medication date. For this study, all medication reported are considered as concomitant medication.

Concomitant medication usage is summarized by the number and proportion of subjects receiving each medication within each therapeutic class using the safety population. Multiple drug usage by a patient is counted only once.

10 EFFICACY ANALYSES

Descriptive analyses will be performed for all subjects.

10.1 ANALYSES OF EFFICACY ENDPOINTS

The following efficacy endpoints based on the observed data will be summarized at the analysis visits in Section 13.1:

- Mean Hb values over selected time ; mean Hb overlay mean weekly roxadustate dose over time plot.
- Number (%) of subjects with mean Hb at ≥ 10 g/dL averaged over selected time periods
- Number of rescue therapy events (composite of transfusions, IV iron, ESAs) of total PEY (defined as the sum of all subject's individual PEY) and number of individual rescue therapy modalities of total PEY (this can be expressed as per 100 PEY dependent on the magnitude of the result). PEY is defined as $(\text{last dose date} - \text{first dose date} + 1) / 365.25$
- Mean monthly oral iron dose (note the monthly dose is defined as sum of weekly dose over 4 weeks) at specific time periods
- Mean Reticulocyte hemoglobin content (CHr) at selected time points
- Mean Highly sensitive C-reactive protein (hs-CRP) at selected time points
- Mean Hepcidin levels in serum at selected time points
- Mean eGFR at selected time points
- Mean Total Cholesterol, LDL cholesterol, LDL/HDL ratio, HDL cholesterol, non-HDL cholesterol at selected time points

- Mean TSAT and Ferritin at selected time points

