Statistical Methods:	All subjects who have received any dose of study treatment will be included in the safety analyses. The efficacy population will include all subjects who receive any study treatment and have non-missing Hb measurement at Baseline and at least one non-missing post-baseline Hb measurement. Monthly mean Hb values will be computed based on the average of Hb values within a 4-week period, and Hb data will be summarized accordingly over time. Hb values within 28 days of known gastrointestinal bleeding, substantial surgical blood loss, or receipt of rescue therapy of IV iron, red blood cell (RBC) transfusion, or ESA, will be censored in efficacy analysis. A last-observation-carried-forward (LOCF) method may be used to impute any missing Hb values. Continuous endpoints will be summarized descriptively by number of subjects (N), mean, standard deviation, median, minimum (min), and maximum (max) values. Categorical endpoints will be summarized descriptively by count and percentage. Safety data will be tabulated using descriptive statistics.

This study will be conducted in accordance with the guidelines of Good Clinical Practice (GCP) and the applicable regulatory requirement(s), including the archiving of essential documents.

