3. ENDPOINTS AND ASSESSMENTS

3.1. Efficacy

The efficacy endpoints in this study are:

- Mean monthly Hb values over time;
- Number (%) of subjects maintaining monthly (monthly defined as a 4-week interval) mean Hb at ≥ 10 g/dL during study participation upon correction (correction is defined as having achieved 2 consecutive Hb values of ≥ 10 g/dL);
- Number (%) of subjects maintaining Hb between 10-13 g/dL for at least 60% of scheduled Hb assessments after the first Hb value is 10 g/dL or higher.
- Composite rate of summarized rescue therapy events (transfusions, IV iron, ESAs) and rate of individual rescue therapy events;
- Number (%) of subjects with phlebotomies;
- Roxadustat weekly total doses over time;
- Dose adjustment frequencies;
- Hb variability;
- Number (%) of subjects withdrawn from the study due to inadequate efficacy.

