4.4.3. Rescue Medication

If a subject is not responding adequately to roxadustat, and rescue therapy is considered a medical necessity by the investigator, rescue therapy will be allowed for a subject provided this has been discussed with the study medical monitor, or is deemed to be an immediate medical necessity by the investigator.

The three options for rescue therapy are as follows:

1. Blood transfusion: For subjects undergoing rescue therapy with transfusion, administration of study medication may continue.
2. Iron supplementation: Oral iron should be the first-line option for iron supplementation. IV iron supplementation may be considered if the following criteria are met:

- The subject has not responded adequately to 2 or more dose increases or reached the maximum dose limit and
- Ferritin saturation is <50 ng/ml **or** transferrin saturation (TSAT) is <10%

OR

- The subject is intolerant of oral iron therapy and
- Ferritin saturation is <50 ng/ml **or** TSAT is <10%

Roxadustat treatment should continue during oral and IV iron supplementation. The investigator may discontinue IV iron supplementation once he no longer considers the subject to be iron deficient. The investigator should carefully monitor the subject's Hb response after the IV iron supplementation.

3. ESAs: ESAs are not to be concurrently administered with. Once a subject is considered a treatment failure due to a lack of efficacy and/or lack of tolerability, and ESA treatment is initiated per the treating physician, roxadustat must be permanently discontinued and the subject also is to be discontinued from the study. In the event of an extenuating circumstance during which a subject inadvertently receives an ESA for a short period of time (e.g., recent bleeding, disruption of dosing due to hospitalization or vacation, etc.), the study medical monitor should be contacted to evaluate the appropriateness of continuing treatment with roxadustat.

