10.7. Statistical Analysis Plan

A detailed Statistical Analysis Plan (SAP) will be finalized prior to data analysis. Any significant changes to the analyses described in this protocol will be highlighted in the SAP. Deviations in analyses from the SAP will be detailed in the clinical study report.

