5.3 ADDITIONAL DATA HANDLING RULES AND PRESENTATION SPECIFICATIONS

The following general guidelines apply to all statistical analyses and data presentations:

- The baseline Hb value for efficacy analysis is defined as the mean of the central laboratory Hb value from the baseline visit at Day 1 (prior to receiving the first dose of study drug in this study), plus any other central lab Hb values within 15 days prior to Day 1
- Baseline of other assessments is defined as the last available value obtained prior to the first dose of study drug in this study, unless otherwise specified in this SAP.
- Analysis visits (instead of the nominal visits from CRF) derived from visit dates and visit time windows are used in all analyses, tables, listings and figures. Unscheduled visits within an allowable window are grouped into the closest scheduled visits based on the visit window specified in Appendix 1. For subjects who have more than one measurement at a scheduled visit, the last measurement issued, with the exception of CPK, WBC, liver function tests (i.e., ALT, AST, GGT, ALP, and total bilirubin), in which the maximum measurement issued.
- By default, US conventional units are used for laboratory value presentations. A set of lab summary tables in SI units are also provided based on TLF index.
- Age is calculated as of date that the informed consent form was signed.
 - age = INTCK('YEAR', Birth Date, Date of Informed Consent, 'C')where INTCK is a SAS function.
- Body weight, height and temperatures are converted using the following formula:
 - kg = lb/2.2
 - cm = 2.54 x in
 - C° = (5/9) x (F° – 32)
- For continuous variables that are recorded as “<X” or “>X”, the value of “X” issued in the calculation of summary statistics.
- The mean, standard deviation and median is presented with adding one more decimal to raw data with rounding off. The minimum and maximum is presented with the same number of decimals as in the raw data.
- All percentages are rounded to one decimal place and lined up by the decimal place. The percentage is suppressed when the count is zero.
- Any p-values are rounded to four decimal places and presented as ‘<.0001’ if they are less than 0.0001 before rounding.
- All tables and listings have a header showing “FibroGen, Inc.”, the protocol number, date of the database transfer, and Page x of y. A footer shows the program file path/name, output file path/name, run date and run time.

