6 SUBJECT ACCOUNTABILITY AND DISPOSITION

Number and percent of subjects are summarized by discontinuation reason.

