13.7 MISSING DATE IMPUTATION FOR PRIOR OR CONCOMITANT MEDICATIONS

For prior or concomitant medications, including rescue medications, incomplete (i.e., partially missing) start date and/or stop date is imputed. When the start date and the stop date are both incomplete for a patient, impute the start date first.

- **Incomplete Start Date**

The following rules are applied to impute the missing start date. If the stop date is complete and the imputed start date is after the stop date, then the start date is imputed using the stop date.

Missing day and month

If the year of the incomplete start date is the same as the year of the first study drug dose date , then the day and month of the first dose is assigned to the missing fields.

If the year of the incomplete start date is not the same as the first dose date , then January 1 is assigned to the missing fields.

Missing month only

Treat day as missing and replace both month and day according to the above procedure.

Missing day only

If the month and year of the incomplete start date are the same as the month and year of the first dose date, then the day of the first dose date is assigned to the missing day.

If the month and year of the incomplete start date are the same as the first dose date, then the first day of the month is assigned to the missing day.

- **Incomplete Stop Date**

The following rules are applied to impute the missing stop date, if needed. If the last dose date is missing, impute it with the last visit date. If the imputed stop date is before the start date (imputed or non-imputed start date), then the imputed stop date is replaced with the start date.

Missing day and month

If the year of the incomplete stop date is the same as the year of the last dose date, then the day and month of the last dose date is assigned to the missing fields.

If the year of the incomplete stop date is not the same as the year of the last dose date , then December 31 is assigned to the missing fields.

Missing month only

Treat day as missing and replace both month and day according to the above procedure.

Missing day only

If the month and year of the incomplete stop date are the same as the month and year of the last dose date, then the day of the last dose date is assigned to the missing day.

If the month and year of the incomplete stop date are not the same as the month and year of the last dose date, then the last day of the month is assigned to the missing day.

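### The SAP drops, without saying so, the protocol's rule that removes hemoglobin values within 28 days of bleeding or rescue from the efficacy analysis

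*SAP*

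**What the plan says.** **Protocol.** The synopsis, under Statistical Methods, commits to censoring. Hb within 28 days of a known gastrointestinal bleed, substantial blood loss at surgery, or "receipt of rescue therapy of IV iron, red blood cell (RBC) transfusion, or ESA, will be censored in efficacy analysis". The same paragraph makes last-observation-carried-forward only optional. Sections 10.6 and 10.6.2 do not repeat the censoring rule, and nothing in them withdraws it. Section 10.7 adds: "Any significant changes to the analyses described in this protocol will be highlighted in the SAP".

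**SAP.** Section 10.1 opens with: "The following efficacy endpoints based on the observed data will be summarized at the analysis visits in Section 13.1". The endpoints that follow include mean Hb and the number and percentage of subjects whose period mean is at least 10 g/dL. Section 5.1 includes every subject who entered the study. Section 5.3 assigns unscheduled results to the nearest scheduled visit and says: "For subjects who have more than one measurement at a scheduled visit, the last measurement issued". Rescue therapy appears as an event rate per patient-exposure-year (section 10.1) and in the date rules of section 13.7: "For prior or concomitant medications, including rescue medications, incomplete (i.e., partially missing) start date and/or stop date is imputed".

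**Treatment after rescue.** Protocol 4.4.3 says: "For subjects undergoing rescue therapy with transfusion, administration of study medication may continue". It also has roxadustat continue during IV iron, and lets the medical monitor consider continuation after a short, inadvertent ESA exposure.

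**The concern.** The primary objective is long-term maintenance of Hb. The study has one arm, no control group and 15 subjects, so mean Hb and the percentage at or above 10 g/dL are its main evidence of efficacy. The protocol's rule keeps out of those summaries any Hb that reflects a transfusion, IV iron, an ESA or a bleed more than the study drug. Without it, values after rescue tend to raise the result, while values around a bleed or just before rescue tend to lower it. Someone who has read the protocol would assume that these values had been removed.

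Two smaller gaps lie close by. SAP 10.1 does not give the denominator for the 10 g/dL percentage at each visit. The protocol 3.1 endpoint "Number (%) of subjects withdrawn from the study due to inadequate efficacy" is missing from the SAP endpoint list, although SAP section 6 still says: "Number and percent of subjects are summarized by discontinuation reason".

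**Working it through.** The plan states no power, alpha or derived sample size, so there is no figure to reproduce. The check compares the texts and then sizes the consequence for one affected subject.

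**Step 1. Is the rule anywhere in the SAP?**

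| Place | Rule on Hb near bleeding or rescue |
|---|---|
| Protocol synopsis, Statistical Methods | Censored, 28 days, mandatory wording |
| Protocol 10.6 and 10.6.2 | Silent |
| SAP 5.1 to 5.3 | Silent; all subjects included |
| SAP 10 and 10.1 | Silent; observed data summarised |
| SAP 13.1 to 13.9 | Silent; only partial rescue dates handled |
| SAP, any section listing changes from the protocol | None in the supplied text |

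**Step 2. Can affected values reach the tables?** Yes. Treatment may continue after transfusion and should continue during IV iron (protocol 4.4.3). Analysis visits run to the last day of treatment (SAP 13.1). For Hb they are Weeks 4, 8 and 12, then every 12 weeks, and the last result in a window stands for the visit (SAP 5.3). One post-transfusion Hb can therefore represent a subject for a 12-week window.

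**Step 3. Effect on mean Hb.** Input from SAP section 3: n = 15. Assumption: the event moves the affected Hb by 1 to 2 g/dL, up after rescue or down after a bleed.

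- Affected value is the one used for the visit: 1/15 = 0.067 to 2/15 = 0.133 g/dL.
- Affected value is one of three 4-weekly values averaged over 12 weeks: (1/3)/15 = 0.022 to (2/3)/15 = 0.044 g/dL.
- Two of the three values affected: (2/3)/15 = 0.044 to (4/3)/15 = 0.089 g/dL.

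**Step 4. Effect on the percentage at or above 10 g/dL.** The Hb values here are constructed examples.

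- After transfusion: (9.6 + 9.6 + 11.0)/3 = 10.07, which counts. Without the 11.0 the mean is 9.6, which does not.
- After a bleed: (10.4 + 10.4 + 8.8)/3 = 9.87, which does not count. Without the 8.8 the mean is 10.4, which does.
- Each reclassified subject is 1/15 = 6.7 percentage points. For example, 14/15 = 93.3% (exact 95% CI 68.1 to 99.8) against 13/15 = 86.7% (59.5 to 98.3).

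**Step 5. How many scheduled values would the rule remove per event?** These are counts over every possible position of the event on the visit grid.

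| Visit interval | Days 0 to +28 | Days -28 to +28 |
|---|---|---|
| 4 weeks | 1 to 2 | 2 to 3 |
| 2 weeks | 2 to 3 | 4 to 5 |

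Both intervals are shown because SAP section 3 describes 2-weekly visits during the first 104 weeks of treatment and 4-weekly visits afterwards.

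**The case against.** The case for a lower weight has several parts.

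- **The rule is only in the synopsis.** The SAP agrees with the protocol's statistics section, which has no censoring. This is true, and the protocol should be reconciled with itself. But that section is silent and does not contradict the synopsis, so the commitment remains.
- **Observed data may just mean no carrying forward of values.** This is plausible, given the LOCF option in the protocol. It still leaves no instruction to exclude anything.
- **The rule may be in the table specifications.** SAP section 1 places these in a separate document, which was not available for this review. However, the SAP sets out its data-handling conventions in its own Appendix 1, including partial rescue dates, and this rule is not there.
- **There may have been no events.** The documents give no counts, and with no events nothing changes. The rule should not depend on the count, and if there were none the fix changes no result.
- **The study is descriptive and reports rescue separately.** This limits the harm: no hypothesis test is affected, the two intervals in the example overlap almost entirely, and rescue rates will appear beside Hb. A separate rescue rate does not show which Hb values were affected.
- **The figures rest on choices.** The Hb examples were built to cross 10 g/dL, and n = 15 is assumed at every visit. Both points stand. With fewer subjects at later visits, each per-subject effect grows in proportion to 15/n.
- **Bleeding and surgical losses are harder to identify than rescue drugs.** This also stands. The protocol does not define substantial surgical loss, and a choice made late would be made with open-label Hb already visible.

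**Conclusion.** The concern holds. A mandatory protocol rule on the main efficacy variable is missing from the SAP, and the omission is not highlighted as protocol 10.7 requires. A programmer following the SAP would keep values that the protocol says to remove.

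The actual size is unknown because no event counts are given. Per affected subject, at n = 15 and with an assumed Hb change of 1 to 2 g/dL, the visit mean moves by 0.07 to 0.13 g/dL when the affected result is the visit value. It moves by 0.02 to 0.09 g/dL when one or two of three values are affected and averaged. Each reclassified subject moves the 10 g/dL percentage by 6.7 points. The net direction cannot be predicted.

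This should be fixed, but it does not undermine the study. Keeping all values is a legitimate choice if the SAP states it with a reason. The denominator and the inadequate-efficacy count are secondary, and the conclusion does not depend on them.

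**What to change.** 1. **Restore the rule in SAP 10.1.** Suggested text: *For mean Hb and the 10 g/dL endpoint, the main summary leaves out central-laboratory Hb within 28 days of a known GI bleed, substantial surgical blood loss, or rescue with IV iron, RBC transfusion or ESA. The same tables with all values are given as a sensitivity analysis.*
2. **Make it programmable.** State whether the 28 days run only after the event or on both sides. Set a criterion for substantial surgical loss, and list the qualifying bleeding and surgical events by subject before any tables are run.
3. **If the sponsor means to drop the rule,** say so in the SAP as a change from the protocol, with the reason.
4. **Reconcile the protocol.** Bring the synopsis and section 10.6.2 into line.
5. **State the denominator** of the 10 g/dL percentage at each visit, and report the number withdrawn for inadequate efficacy from the disposition data in SAP section 6.
6. **Optional improvement, not a protocol rule.** Add a supportive table out of all 15 subjects with three rows: maintained; not maintained, including exits for lack of efficacy or ESA use; and not assessable, for other exits or no usable Hb.

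**Cost.** SAP wording, one Hb exclusion flag and a short event listing. SAP 13.7 already covers incomplete dates of rescue medications; bleeding and surgical events need a separate review. The rule removes 1 to 5 scheduled Hb values per event, depending on the visit interval and the direction of the window. The reported percentage may go up or down.

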10.6.2. Efficacy Analyses

Hemoglobin results obtained from the central laboratory will be used for all efficacy analyses.

Baseline Hb value for efficacy analysis is defined as the mean of the central laboratory Hb value from the Baseline Visit Day 1 (prior to receiving the first dose of study drug in this study), plus any other central laboratory Hb values obtained within 15 days prior to Day 1. Baseline eGFR, ferritin, TSAT, and other efficacy endpoints are defined as the last value prior to the first dose of study treatment.

All efficacy analyses will be based on the EE population.

- Monthly mean Hb values and changes from baseline will be summarized descriptively for the Dialysis, Non-Dialysis, and Newly Initiated populations at each scheduled time point as well as monthly
- The number (%) of subjects maintaining Hb ≥ 10 g/dL during study participation, the composite rate of summarized rescue therapy events (transfusions, IV iron, ESAs) and rate of individual rescue therapy events, and the number (%) of subjects receiving phlebotomies will be summarized for the Dialysis, Non Dialysis and Newly Initiated populations
- The dose level at the time of Hb response will be summarized descriptively
- The frequency of dose increases and decreases and use of rescue therapy will also be tabulated. Median time to Hb response will be estimated for each subject previously receiving placebo (Newly Initiated group) using the Kaplan-Meier method. Hemoglobin response is defined as a Hb increase from baseline of at least 1.0 g/dL. In addition, median initial responsive time and dose will be tabulated to evaluate when an initial Hb change from baseline reaches at least 1.0 g/dL. Number (%) of

subjects, scheduled Hb values, and consecutive Hb values achieved for a variety of Hb ranges between 11.0 and 13.0 g/dL, as well as above or below these ranges, during 4-week study intervals throughout the treatment period will be tabulated.

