8 STUDY MEDICATION

8.1 EXTENT OF EXPOSURE AND DOSE ADMINISTRATION

Treatment duration, the Patient-Exposure-Year (PEY) are defined as (Last Dose Date – First Dose Date + 1)/365.25, during this study.

Average weekly study dose (in mg or mg/kg) are summarized for selected time periods such as every 4 weeks, from week 0 – 24, every 8 weeks, from week 25-48, and every 12 weeks, starting week 49 through EOT/ET.

Dose adjustment frequencies (number (%)) of subjects with a dose increase, dose decrease, dose hold, separately)

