13 APPENDIX 1: DATA HANDLING CONVENTIONS**13.1 VISIT TIME WINDOWS**

| Endpoint | Visits during Treatment Period | | | | |
|---|--------------------------------|-----------------------------|----------------------|---|------------------------------------|
| | Every 4 weeks ^a | Every 24 weeks ^b | Target Day | Analysis Visit Windows Actual Assessment Day ⁺ | Analysis Visit ⁺⁺ |
| | | | Day 1 | Day 1 | Baseline |
| BP, HR, respiratory rate* | X | | Day 7 * (Week #) + 1 | Target Day plus or minus half the duration to the next Target Day | Weeks 4, 8, 12 then every 12 weeks |
| 12-lead ECG | | X | Day 7 * (Week #) + 1 | [Target Day – 84, Target Day + 83] | Week 24, 48, ... |
| Hb, reticulocyte count, CHr* | X | | Day 7 * (Week #) + 1 | Target Day plus or minus half the duration to the next Target Day | Weeks 4, 8, 12 then every 12 weeks |
| CBC with WBC differential * | X | | Day 7 * (Week #) + 1 | Target Day plus or minus half the duration to the next Target Day | Weeks 4, 8, 12 then every 12 weeks |
| Fasting serum chemistry (including LFTs, lipid panel, glucose) | X | | Day 7 * (Week #) + 1 | Target Day plus or minus half the duration to the next Target Day | Weeks 4, 8, 12 then every 12 weeks |
| Serum iron, ferritin, transferrin (or TIBC), TSAT | X | | Day 7 * (Week #) + 1 | Target Day plus or minus half the duration to the next Target Day | Weeks 4, 8, 12 then every 12 weeks |
| Special labs (CHr, hepcidin, hs-CRP, plus exploratory biomarkers) ^l | | X | Day 7 * (Week #) + 1 | [Target Day – 42, Target Day + 41] | Week 24, 48, ... |
| 
Abbreviations: BP = blood pressure; CBC = complete blood count; CHr = reticulocyte hemoglobin content; CRP = C-reactive protein; ECG = electrocardiogram; HR = heart rate; LFT = liver function test; TIBC = total iron binding capacity; TSAT = transferrin saturation; WBC = white blood cell.
 
* Visit weeks are weekly (week 1 to 4), every 2 weeks (week 6 to 24), every 4 weeks afterwards
 
a Visit weeks may include of: Weeks 13, 37, 61, 85, 109, 133, 157, 181, 205, 229, and 253
 
b Visit weeks may include of: Weeks 25, 49, 73, 97, 121, 145, 169, 193, 217 and 241
 
++ Analysis visits are up to the EOT, which is the last day of treatment.
 
Note: The lower bound for the first visit window starts at Day 1.
 | | | | | |

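### After Week 12 the SAP reports Hb at 12-week visits where the protocol endpoints use 4-week means; the change is not marked and the value within a window is left undefined

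*SAP*

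**What the plan says.** **Protocol.** Section 3.1 lists mean monthly Hb over time and "Number (%) of subjects maintaining monthly (monthly defined as a 4-week interval) mean Hb at ≥ 10 g/dL during study participation upon correction". The statistical methods in the synopsis fix the unit: "Monthly mean Hb values will be computed based on the average of Hb values within a 4-week period". Section 10.6.2 asks for monthly mean Hb and its change from baseline "at each scheduled time point as well as monthly". Section 10.7 requires the SAP to highlight any significant change to the protocol's analyses.

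**SAP, Hb.** Section 10.1 opens with "The following efficacy endpoints based on the observed data will be summarized at the analysis visits in Section 13.1". The list includes mean Hb, the number (%) of subjects with mean Hb of at least 10 g/dL averaged over periods whose length is not given, and a plot described as "mean Hb overlay mean weekly roxadustate dose over time plot". In 13.1 the Hb analysis visits are "Weeks 4, 8, 12 then every 12 weeks", and each window reaches half the distance to the next target day on either side. A footnote there shows Hb still being collected at least every 4 weeks.

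**SAP, several values in one window.** Section 5.3 takes the last measurement, except for CPK, WBC and liver tests, where it takes the maximum. Hb is not among the exceptions.

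**SAP, dose.** Section 8.1 summarises average weekly dose over periods that it introduces as examples: "every 4 weeks, from week 0 – 24, every 8 weeks, from week 25-48, and every 12 weeks, starting week 49 through EOT/ET".

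**The concern.** Maintenance of Hb is the primary objective, and the protocol judges it month by month for each subject. The SAP reports one Hb result per 12 weeks for most of a study planned to last up to 312 weeks. It also drops the per-subject requirement that Hb stay at or above 10 g/dL after correction. A subject who falls below 10 for one month fails the protocol endpoint, but may leave no trace in the SAP's tables. None of SAP sections 1 to 13 identifies this as a change, so a reader of the results could take the SAP percentage for the protocol endpoint.

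The secondary objective concerns doses and dose adjustments, and dose is reviewed against Hb every 4 weeks (protocol 4.3.2 and Appendix C). The overlay plot can show that relation only if Hb and dose refer to the same periods, and the SAP does not say that they do.

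**Working it through.** The study has no power calculation, so there is no sample-size figure to reproduce. The check compares time grids and then asks what can be lost.

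**1. Number of results per subject.** Over 312 weeks (SAP 3) the protocol unit gives 312 / 4 = 78 intervals. SAP 13.1 gives Weeks 4, 8 and 12, then Weeks 24 to 312 in steps of 12: 3 + [(312 − 24) / 12 + 1] = 3 + 25 = 28 visits.

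**2. Window width.** Target day = 7 × week + 1. From Week 24 targets are 84 days apart, so the half-width is 42 days. Week 24 covers days 127–210 and Week 60 covers days 379–462. Each window holds 84 / 28 = 3 four-week values if Hb is measured every 4 weeks. Earlier windows also need care. Read literally, Week 12 is 85 ± 42 = days 43–127, which contains all of Week 8 (57 ± 14 = days 43–71).

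**3. What a window can hide.** Take 4-week values of 10.3, 9.4 and 10.3.
- Protocol: the second month is below 10, so the subject does not maintain.
- SAP, window mean: (10.3 + 9.4 + 10.3) / 3 = 10.0, counted as at least 10.
- SAP, last value: 10.3, counted as at least 10.

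**4. Direction for the per-subject endpoint.** Assume one Hb value per 4 weeks and windows holding only values after correction. If every 4-week value is at least 10, then every window mean and every last value is at least 10. The converse fails, as step 3 shows. So the SAP grid can only keep or raise the number counted as maintaining. With 15 subjects (SAP 3), one reclassified subject is 100 / 15 = 6.7 percentage points.

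**5. Direction for per-period percentages.** This needs assumptions that the documents do not supply: normal 4-week values, within-subject SD 0.7 g/dL and lag-1 correlation ρ of 0 or 0.5. The SD of a mean of three values is 0.7 × √[(3 + 4ρ + 2ρ²) / 9], which is 0.404 for ρ = 0 and 0.547 for ρ = 0.5.

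| Subject's long-run mean | 4-week value below 10 | 12-week mean below 10 (ρ = 0; ρ = 0.5) |
|---|---|---|
| 10.5 | 24% | 11%; 18% |
| 9.8 | 61% | 69%; 64% |

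Window averaging is favourable when the subject's mean is above 10 and unfavourable when it is below. Under the last-value reading, the expected percentage equals that of any single 4-week value (24% or 61%). There is no average shift, but two of the three values go unused.

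**6. How often a dip is lost (illustration).** Three 4-week values per window were simulated with mean 10.5–11.5, SD 0.6–1.0 and ρ of 0 or 0.5. Among windows with at least one value below 10, the window mean was still at least 10 in 54% to almost 100%, and the last value was at least 10 in 45% to 68%. At mean 11, SD 0.8 and ρ = 0.5, 24.0% of windows contained a dip and 5.5% had a mean below 10, so 1 − 5.5/24.0 = 77% of the dips were hidden. The last value hid 56%.

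**7. Hb against dose, if the 8.1 example periods were plotted.** Weeks 49–60 are days 337–420 and Weeks 61–72 are days 421–504. The Week 60 Hb window, days 379–462, shares 42 days with each (379–420 and 421–462). The same 42/42 split recurs at every later visit.

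**The case against.** Three stronger readings are tempting, and the documents support none of them.

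- **A reader might infer that Hb is definitely averaged over 12 weeks.** The SAP never says so. Section 10.1 speaks of averaging over undefined periods, while 5.3 would take the last measurement, in which case mean Hb is simply a mean across subjects at a visit. The text is ambiguous. What stands is that neither reading yields the protocol's 4-week mean.
- **A reader might infer that the overlay pairs Hb with dose from different weeks.** The 8.1 periods are only examples. The lead-in to 10.1 points to 13.1, which has no dose row. Specifications for figures are in a separate document (SAP 1). The supportable statement is that the plot's dose intervals are not specified in the SAP.
- **A reader might infer that the reported percentage is biased upward.** For per-period percentages this depends on the subject's mean and on the reading of the SAP (step 5). The one-directional statement holds only for the per-subject endpoint under the conditions in step 4. Where Hb is measured more often than every 4 weeks, exceptions are possible.

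One can also say that the study is small, uncontrolled and descriptive, that no test or threshold depends on this percentage, that a sustained fall would still show, and that a 12-week display is reasonable over six years. All of that is fair, and it limits the consequence. It does not explain why the protocol's endpoint is absent or why the change is unmarked. The simulation also ignores dose titration in response to low Hb, so its percentages are illustrations only.

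**Conclusion.** The departure is established by the text. Protocol 3.1, 10.6.2 and the synopsis use 4-week means. SAP 10.1 and 13.1 report Hb on 84-day windows from Week 24, giving 28 results where the protocol unit gives 78, and the SAP does not highlight this. It also contradicts itself on whether a window's Hb is a mean or the last value, and on either reading a one-month fall below 10 g/dL can disappear.

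With one Hb value per 4 weeks, the effect on the number maintaining at least 10 is zero or upward, in steps of 6.7 points for 15 subjects. How many steps cannot be derived from the documents. The overlay's dose grid is a gap in the specification; the 42/42 split arises only if the 8.1 examples are used. The point should be corrected, but in a descriptive study it does not undermine the study as a whole.

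**What to change.** In the SAP:

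1. In 10.1 and 13.1, define Hb for efficacy as the mean in consecutive, non-overlapping 4-week intervals over the whole treatment period.
2. From these intervals report both the protocol's per-subject endpoint (4-week mean kept at or above 10 g/dL after correction) and the percentage at or above 10 in each interval. The per-interval percentage alone does not restore the protocol endpoint.
3. Keep any 12-week display only as a supplement built from the 4-week means.
4. State that the last-value rule in 5.3 does not apply to Hb efficacy endpoints.
5. Use the same intervals, with the same start and end days, for weekly dose in the overlay plot.
6. Record any remaining departure from the protocol, as protocol 10.7 requires.

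No new data are needed, because Hb is already collected at least every 4 weeks. The cost is SAP wording, longer tables, and percentages that are noisier and possibly slightly lower with 15 subjects.
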